9.5.4 Participants treated with anticoagulant therapy

Evaluate the accuracy and usefulness of CDR and D-dimer testing in participants with a suspected recurrent VTE who are receiving therapeutic anticoagulant therapy.

9.5.5 Compare indeterminate imaging results in participants with and without available information about previous imaging

We will compare the proportion of participants with indeterminate results in participants with and without available baseline imaging. We will assess how these participants were managed (treated vs. not treated). Of the participants who were not treated we will evaluate the 3 months VTE failure rate.

10. DATA COLLECTION AND QUALITY ASSURANCE

10.1 Data Collection Forms

Data collection is the responsibility of the designated research study staff at the clinical centre under the supervision of the local Investigator. During the study, the Investigator must maintain complete and accurate documentation for the study. Study Case Report Forms (CRFs) are designed to record the disease status,

treatment, observations, follow-up and other pertinent data on each enrolled study participant. Participants will be identified by a unique study ID number. Data reported on the CRF derived from source documents must be consistent with the source documents. All source documents and laboratory reports must be reviewed by the designated research study staff at the participating clinical centre.

10.2 Data Management

Data management will be performed using a web-based system designed by the OHRI Data Management Services. Only trained research personnel from each site will have authorization with an access password to enter and modify electronic case report forms (eCRFs). The web based system functions with a secure server and backups will be done regularly. A user tracking system will track the date and time that users enter or modify data. Once eCRFs are completed, data verification may result in additional requests to clarify the data.

10.3 Retention of Study Records

To enable future evaluations and audits, the local investigator must maintain confidential study documentation and ensure the retention of the study documents for a minimum of 10 years, as per OHRI, the sponsor. Study documents will include the identity of all study participants (sufficient information to link records, e.g., eCRFs and hospital records); all original signed Informed Consent Forms, and source documents.

After a minimum of 10 years, all study documents will be destroyed (via incineration or shredding) at the local site.

10.4 Quality Assurance

Study related procedures must be conducted in compliance with the protocol, amendments, regulations and guidelines, in order to ensure data integrity. Any deviations from the protocol will be accurately documented, reported and reconciled.

Protocol deviations refer to incidents involving non-compliance with the protocol that are unlikely to have a significant impact on the on data integrity.

If a protocol deviation occurs the following procedures will be followed:

- The local investigator or delegate will document and explain any deviation from the approved protocol
- Deviations from the protocol must be reported in the study source document
- Deviations will be reviewed during monitoring visits.
- A log of all deviations at the site must be maintained (ideally in an excel spreadsheet)

As this is an observational study that does not affect patient safety, there will be no protocol violations to collect.

11. PARTICIPANT RIGHTS AND CONFIDENTIALITY

11.1 Research Ethics Board

This study will be reviewed and approved by the Ottawa Health Science Network Research Ethics Board before commencement of the study. Each participating site must also obtain Ethics Board approval before study initiation. Annual ongoing review will also be performed. Any amendment to the protocol or informed consent form must be approved by the local Research Ethics Board before implementation.

11.2 Informed Consent Forms

Prior to inclusion in the study, the investigator, or his designee, will provide each participant (or the participant's acceptable representative), full and adequate verbal and written information regarding the objectives and procedures of the study and the possible risks involved. The participants must be informed about their right to withdraw from the study at any time. Written participant information will be given to each participant before enrolment. The investigator or his designee will obtain signed informed consent (or witnessed verbal consent according to applicable regulations) from all participants prior to inclusion in the study.

11.3 Participant Confidentiality

To protect the participant's confidentiality, source documents containing personal identifiers and informed consent forms will be kept separate from research notes and worksheets. Case report forms will not contain any identifying information. The identification log which links the identification of the participant to the assigned participant code will, according to local policy, be kept in a cabinet under lock and key or on a secure electronic drive.

12. STUDY ORGANIZATION

12.1 Study Coordination

The study will be coordinated through the Thrombosis Research Program, Ottawa Hospital Research Institute (OHRI), located at The Ottawa Hospital General Campus in Ottawa, Ontario. The multicentre coordinator, under the direction of the study Principal Investigator, [name] [name], will be responsible for the overall study management including implementation of study protocol logistics, data management, and quality assurance related to study data. Local coordinators and site investigators will work together to screen, recruit, and follow study participants. Each co-investigator will be responsible for the conduct of the study at their respective sites.

12.2 Central Independent Adjudication Committee (CIAC)

All cases of confirmed VTE will be adjudicated by independent adjudicators. The results of all imaging tests performed at the time of suspected recurrent VTE will be compared with the patient's previous imaging, baseline or index, when available, and will be performed according to the predefined definitions (Refer to **Appendix E**:

Adjudication of Suspected Recurrent VTE Events). The adjudicators will confirm or refute suspected recurrent DVT and PE events.

The adjudication committee will also evaluate secondary outcomes including all suspected VTE events and deaths occurring during the 90 (± 7) day follow-up period. The adjudication results will be the basis for the final analysis.

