Objectives	
Primary Objective: To assess the accuracy and usefulness of the Wells DVT, Wells PE and Geneva clinical decision rules in patients with a clinically suspected recurrent VTE.
 
Secondary Objectives:
 
• To assess the utility of recalibrating the existing clinical decision rules.• To derive a new CDR, specific to patients with a suspected recurrent VTE, and to assess whether this CDR would improve risk stratification as compared with existing CDRs.• To assess the accuracy of D-dimer testing in patients with suspected recurrent VTE both on and off anticoagulation.• To evaluate the accuracy of current CDRs in patients on anticoagulant therapy at the time of suspected recurrent VTE.
Duration	All consecutive eligible patients will be approached for enrolment into this study over 3 years.
Design	This is a multicentre, observational cohort study to prospectively identify potential predictors of recurrent VTE. The predictive value of individual and combined candidate predictors will be evaluated in patients with suspected recurrent VTE. All suspected recurrences will be blindly and independently adjudicated.
Significance	If the newly developed clinical decision rule is proven to accurately determine the pre-test probability in patients with a suspected acute recurrent VTE, it could be integrated in diagnostic strategies that might lower cost, avoid radiation exposure and potentially decrease over-diagnosis of patients with suspected recurrent VTE.

Target Sample Size A total of 745 participants will be enrolled at Canadian sites.

Participant Population

Inclusion Criteria

1. Outpatient with clinically suspected acute recurrent DVT or PE regardless of whether the previous event was a DVT or PE
2. Age ≥ 18 years old
3. Willing and able to give informed consent

Exclusion Criteria

1. Life expectancy less than 3 months
2. Suspicion of upper extremity thrombosis or thrombosis at an unusual site (e.g. cerebral or abdominal venous thrombosis)
3. Previous VTE was distal DVT or subsegmental PE
4. Suspected recurrent VTE is asymptomatic
5. Previously enrolled in this study

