6.3 Follow-up Visits

All patients in whom a recurrent VTE is ruled out will receive a follow-up call at 3 months (90 ± 7 days) after the initial evaluation using a structured interview script. Research coordinators will be trained by the investigator or multicenter coordinator prior to follow-up to ensure consistency in eliciting new signs and symptoms of DVT and PE between sites. Any new leg or chest symptoms reported to study personnel during study follow-up will prompt clinical and diagnostic assessment. Participants with suspected VTE will be assessed in the Thrombosis Clinic (or Emergency Department) and ordered diagnostic testing as judged necessary by their physician or the investigator. If participants report that they sought medical attention for complaints of possible VTE, medical records and imaging results will be collected to prepare an adjudication report. Any participant who seeks medical attention during their follow-up period and is once again not diagnosed with a recurrent VTE will have an additional call at 90 (± 7 days) days after they were last assessed.

All deaths during follow-up will prompt chart review and all available information including interviews with next of kin will be documented to permit preparation of an adjudication report to determine if the death is PE related.

The follow-up period is relatively short and therefore participant loss to follow-up should be minimal. However, for participants that cannot be reached by phone, an exhaustive search will determine if outcome events have occurred (including calls to next of kin or pre-identified contacts, obituary searches, retrieval of death certificates, review local hospital databases) prior to participants being declared lost to follow-up.

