Appendix E: Adjudication of Suspected Recurrent VTE Events

Recurrent VTE

Recurrent VTE will be excluded if participants have a low/intermediate or unlikely pre-test clinical probability with the Geneva or Wells rule and a negative D-dimer test result.

Recurrent Deep Vein Thrombosis

Recurrent DVT will be ruled out if participants have a normal ultrasound (fully compressible veins) or an unchanged/improved incompressible segment as compared with baseline when available.

The criteria for diagnosis of recurrent DVT will be:

1. Compression ultrasound revealing a new (compared to baseline/index ultrasound) area of non compressibility of a venous segment above the trifurcation of the popliteal vein will be considered diagnostic of a deep vein thrombosis.
-OR-
2. Venography demonstrating a constant intraluminal filling defect in the deep veins above the trifurcation of the popliteal vein will be considered diagnostic of a deep vein thrombosis.

Recurrent Pulmonary Embolism

1. If the V/Q scan is normal or unchanged from baseline/index imaging, PE will be considered excluded.
2. If the V/Q scan is non-normal and a new unmatched segmental or greater perfusion defect is documented then recurrent PE will be diagnosed.
3. If a new matched or subsegmental perfusion defect is documented the test won't be considered positive for PE.
4. If participants receive a spiral CT scan and an intraluminal filling defect is seen in a segmental or greater vessel that was previously free of thrombus, pulmonary embolism is diagnosed. If the CT scan is normal or unchanged as compared with baseline, PE will be considered excluded.
5. Pulmonary angiography demonstrating a constant intraluminal filling defect or a cutoff of a vessel > 2.5 mm in diameter will be considered diagnostic for PE.

Death

All deaths during follow-up will be adjudicated as to the likelihood that the death was related to PE. The following criteria will be used: *Certain*: hypotension, hypoxia, cardiac arrest with no other explanation than PE, autopsy or radiographic confirmation; *Highly probable*: criteria for certain but another disease could have caused the death; *Probable*: other cause suspected based on clinical evidence but 100% certainty not available; *Unlikely*: all other cases.

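### Section 12.2 conflicts with the protocol summary, and with itself, on whether index events not confirmed as VTE go to central adjudication

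*Combined protocol and SAP*

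**What the plan says.** **Scope at index.** The Design row of the protocol summary says "All suspected recurrences will be blindly and independently adjudicated". Section 12.2 opens with "All cases of confirmed VTE will be adjudicated by independent adjudicators". The same paragraph goes on: "The results of all imaging tests performed at the time of suspected recurrent VTE will be compared with the patient's previous imaging, baseline or index". That comparison is made only where earlier imaging exists. It then adds: "The adjudicators will confirm or refute suspected recurrent DVT and PE events".

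**Scope in follow-up.** The next paragraph of 12.2 says "The adjudication committee will also evaluate secondary outcomes including all suspected VTE events and deaths occurring during the" 90-day follow-up. Section 6.3 adds that "All patients in whom a recurrent VTE is ruled out will receive a follow-up call at 3 months".

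**Use.** Section 12.2 ends: "The adjudication results will be the basis for the final analysis".

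**Criteria.** Appendix E is titled for suspected events and gives criteria to exclude as well as to diagnose. For DVT: "Recurrent DVT will be ruled out if participants have a normal ultrasound (fully compressible veins) or an unchanged/improved incompressible segment" relative to baseline. It also excludes recurrent VTE where the Wells or Geneva category is below high (or is unlikely) and the D-dimer is negative, with no mention of imaging.

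**Blinding.** Only the summary mentions it. Neither 12.2 nor Appendix E says what adjudicators are blinded to.

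**The concern.** The adjudicated outcome is the reference standard for everything in 9.5: calibration, the c-statistic, and the false-negative rate in participants below high probability with a negative D-dimer. If access to that standard depends on the local conclusion, verification is one-sided. A locally confirmed case can be overturned. A locally excluded or indeterminate case cannot be upgraded at index.

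Some removals can be expected. Section 6.2.3 describes PE as confirmed by a filling defect at subsegmental level or larger on CT, whereas Appendix E asks for segmental or larger. Those two passages need reconciling in their own right. Under the narrow reading of 12.2, nothing at index balances such removals.

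The cases most in need of central review are also the ones at risk of being left out. The background stresses how hard it is to separate new from residual thrombus and cites a study with 32% inconclusive ultrasounds in suspected ipsilateral recurrence. Section 9.5.5 expects indeterminate results, some of them untreated. Such participants are not confirmed cases, so the first sentence of 12.2 would not send them.

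**Working it through.** **Inputs (section 9.2).** 100 confirmed DVT and 100 confirmed PE are required; the confirmation rates are 29% and 25%.

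**The plan's own figure.** N = events / confirmation rate, rounded up.
- DVT: 100 / 0.29 = 344.8, so 345
- PE: 100 / 0.25 = 400
- Total: 345 + 400 = 745, which reproduces the plan

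**How many index events each wording covers.**
- Summary: 745
- First sentence of 12.2: 345 × 0.29 + 400 × 0.25 = 100 + 100 = about 200 (27%)
- Difference: 745 − 200 = 545 (73%), made up of 245 suspected DVT and 300 suspected PE

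**Events affected under the narrow reading.** The documents give no rate of VTE missed locally, so this is an assumed range. Missed = rate × 545; share of all true VTE = missed / (200 + missed).

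| Assumed missed rate | Missed events | Share of true VTE |
|---|---|---|
| 0.5% | 2.7 | 1.3% |
| 1% | 5.4 | 2.7% |
| 2% | 10.9 | 5.2% |
| 5% | 27.2 | 12.0% |

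**How sensitive the false-negative rate is.** The D-dimer review in section 2.2 puts the rule-out group at 10–16% of patients. Applied to 745 this is about 74 to 119 participants. Exact (Clopper-Pearson) 95% intervals:

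| Group size | 0 events | 1 event |
|---|---|---|
| 74 | upper limit 4.9% | 1.4% (0.03–7.3%) |
| 119 | upper limit 3.1% | 0.8% (0.02–4.6%) |

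One event therefore matters to this estimate, wherever it is found. The table shows sensitivity to a single event. It does not measure the bias caused by 12.2.

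**What follow-up recovers.** Under 6.3, work-up after index is prompted by reported symptoms, a visit for possible VTE, or death. A missed VTE that stays silent for 90 days is not found. Section 12.2 labels follow-up events secondary outcomes, and 9.5 gives no time window for its false-negative rate, so whether a follow-up event counts there is left open. Section 6.3 promises the call to those in whom VTE is ruled out and does not name indeterminate cases, although 9.5.5 plans a three-month failure rate for the untreated ones.

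**The case against.** The strongest reply is that universal index adjudication is already intended and one sentence is loosely worded. The summary, the all-imaging sentence, the confirm-or-refute sentence and Appendix E all point to suspected events, and exclusion criteria would have little purpose if only positives were reviewed. A reader might infer that 12.2 sends only locally confirmed cases. The text contains neither the word *only* nor the word *locally*, and the rest of the paragraph points the other way. This stands: 12.2 is inconsistent, not clearly restrictive. Even so, the later sentences can be read as describing what is done with the cases sent, and the contrast between confirmed VTE at index and all suspected events in follow-up makes the narrow reading a plausible one for a site.

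A reader might also infer that a VTE missed at index can never be found. The 90-day call, the adjudication reports and the review of deaths rule that out; they are an indirect and incomplete route.

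Third, a reader might attribute a shift of about one percentage point in the rule-out group to 12.2. Appendix E does not support that. It excludes VTE on score plus negative D-dimer, so adjudicators applying it to everyone could still return an exclusion in that group.

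Finally, the background regards over-diagnosis as the likelier error in this population, and reviewing positives does address that. It does not justify leaving negatives unreviewed when the outcome is used to judge how safely a rule excludes disease.

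**Conclusion.** The inconsistency is real and concerns the primary reference standard. Read literally, the first sentence of 12.2 leaves about 545 of 745 index events without central review, and index adjudication could then only lower the count of confirmed events. On an assumed 0.5–5% missed among index negatives, about 3 to 27 events (1.3–12.0% of true VTE) would be affected, less whatever follow-up recovers and only if sites take the narrow reading. The figures of 200 and 545 rest on the planning confirmation rates.

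The direction is clear only for event counts and observed rates, which would be too low. The documents do not support a general claim that the existing rules would look better than they are: the effect on the c-statistic depends on which participants are misclassified and is not determined. Nor do they show that local conclusions are drawn knowing the study D-dimer, which 6.2.2 has frozen and assayed centrally in batches.

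**What to change.** 1. **Section 12.2, first sentence.** State that all index suspected events, whether locally confirmed, excluded or indeterminate, are adjudicated on their imaging by adjudicators blind to the rule scores, the D-dimer result and the local conclusion. This brings 12.2 into line with the summary and says what the blinding covers.
2. **Appendix E.** Reconcile that blinding with the criterion that excludes VTE on score plus D-dimer. Adjudicators blind to both cannot apply it, and where imaging was done, the tests under evaluation should not define the reference standard.
3. **Section 9.5.** State that adjudicated 90-day VTE in index negatives counts in the false-negative rate. For participants who had no imaging, this follow-up is the only information on VTE status that does not depend on the index tests.

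**Cost.** Protocol wording, with no change to the sample size of 745. Compared with the literal reading of 12.2, the committee would receive up to about 545 more dossiers; compared with the summary, none. Section 6.2.3 already has all imaging results recorded. The documents do not describe the committee's capacity, so that workload should be confirmed. The change should be made before sites assemble dossiers, because unsent negatives are hard to recover later.

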12.3 Steering Committee

A Steering Committee consisting of the study co-investigators will manage the overall conduct of the study and will meet regularly via teleconference or face to face meetings to monitor study progress, execution, management, analysis and reporting.

15. APPENDICES

Appendix A: Current Clinical Decision Rule for Suspected DVT

Wells Rule for Suspected DVT

[figure not shown]
Clinical characteristics	Points	
Active cancer (patient receiving treatment for cancer within the previous 6 mo or currently receiving palliative treatment)	+ 1	
Paralysis, paresis, or recent plaster immobilization of the lower extremities	+ 1	
Recently bedridden for 3 days or more, or major surgery within the previous 12 wk requiring general or regional anaesthesia	+ 1	
Localized tenderness along the distribution of the deep venous system	+ 1	
Entire leg swollen	+ 1	
Calf swelling at least 3 cm larger than that on the asymptomatic side (measured 10 cm below tibial tuberosity)	+ 1	
Pitting edema confined to the symptomatic leg	+ 1	
Collateral superficial veins (nonvaricose)	+1	
Previously documented deep-vein thrombosis	+1	
Alternative diagnosis at least as likely as deep-vein thrombosis	-2	
Total score	Clinical probability	Prevalence of DVT
< 2 points	DVT unlikely	5.5 % (95%CI: 3.8 to 7.6%)
≥ 2 points	DVT likely	27.9 % (95%CI: 23.9 to 31.8%)

Appendix B: Current Clinical Decision Rules for Suspected PE

Wells Rule for Suspected PE

Wells score		Revised Geneva score			
Active cancer	+ 1	Age > 65 years	+ 1		
Hemoptysis	+ 1	Active cancer	+ 2		
History of previous DVT or PE	+ 1,5	Hemoptysis	+ 2		
Heart rate > 100 /min	+ 1,5	History of previous DVT or PE	+ 3		
Surgery or bedrest \geq 3 days within 1 month	+ 1,5	Surgery or lower limb fracture within one month	+ 2		
Clinical signs or symptoms of DVT	+ 3	Unilateral edema and pain at palpation	+ 4		
No alternative diagnosis as or more likely than PE	+ 3	Spontaneously reported calf pain	+ 3		
		Heart rate			
		75-94 / min	+ 3		
		\geq 95 / min	+ 5		
Clinical Probability	Total Score	Prevalence of PE	Clinical Probability		
Low	< 2	5.7 (3.7-8.2)	Low	0-3	9.0 (7.6-10.6)
Intermediate	2-6	23.2 (18.3-28.4)	Intermediate	4-10	26.2 (24.4-28.0)
High	> 6	49.3 (42.6-56.0)	High	\geq 11	75.7 (69.0-81.8)
Unlikely	\leq 4	8.4 (6.4-10.6)			
Likely	> 4	34.4 (29.4-39.7)			

